9.2 Populations for Analyses

Safety analysis set: The safety analysis set is defined as participants who received any dose of daxdilimab. The efficacy, safety, PD and immunogenicity analyses will be based on the safety analysis set.

PK analysis set: The PK analysis set is defined as participants who received any dose of daxdilimab and have at least 1 measurable PK concentration post dose. The PK analyses will be based on PK analysis set.

9.3 Statistical Analyses

9.3.1 General Approach

Continuous variables will be summarized in tables and will include the number of participants, mean, standard deviation (SD), median, minimum, and maximum. Categorical variables will be presented in tables as frequencies and percentages. Details of the statistical analysis will be specified in a separate statistical analysis plan (SAP).

9.3.2 Efficacy Analyses

9.3.2.1 Analysis of the Primary Efficacy Endpoint

The primary efficacy endpoint of percent change from baseline in SALT score at Week 24 will be summarized using descriptive statistics. A 2-sided 95% confidence interval will be calculated for the mean.

9.3.2.2 Analysis of the Secondary Efficacy Endpoints

The continuous secondary efficacy endpoints will be summarized similarly to the primary efficacy endpoint. The binary secondary efficacy endpoints will be summarized descriptively using frequencies and percentages. A 2-sided 95% confidence interval will be calculated for the percentage.

9.3.2.3 Handling Plan for Prohibited Medication Use

For participants who take prohibited medications that are considered to be effective for treatment of AA, the result after administration of the prohibited medications will be imputed using the worst observation, including baseline for continuous endpoints. The participants will be considered non-responder after administration of the prohibited medications for binary endpoints.

9.3.2.4 Handling Plan for Treatment discontinuation

Participants who discontinue treatment early will be asked to come to scheduled evaluations until the end of the study unless participants withdraw consent of trial participation or are lost to follow-up. The data collected after discontinuation of study treatment will be included in the analysis.

PRIVATE AND CONFIDENTIAL INFORMATION OF HORIZON THERAPEUTICS IRELAND DAC

9.3.2.5 Handling Plan for Missing Data

Missing visits, due to skipped visits or early dropout of study, will have the last observation carried forward for continuous endpoints. The participants will be considered non-responders after early dropout of study for binary endpoints.

9.3.3 Safety Analyses

AEs will be coded using the most recent version of Medical Dictionary for Regulatory Activities (MedDRA). Treatment emergent AEs will be summarized by the number of participants reporting the events, as well as by System Organ Class (SOC), Preferred Term (PT), severity, seriousness, and relationship to IP. For the summary of AEs by severity, each participant will be counted only once within a System Organ Class or a Preferred Term by using the AEs with the highest intensity within each category. For the summary of AEs by relationship to IP, each participant will be counted only once within a SOC or a PT by using the AEs with the greatest reported relationship within each category. The number and percentage of participants reporting treatment-emergent SAEs and treatment-emergent AESIs will also be summarized.

Clinically significant changes in laboratory analyses, vital signs, ECGs, and new findings on physical examination will be recorded as AEs or SAEs. Laboratory assessments, vital signs, and ECGs, as well as their changes from Baseline at each visit will also be summarized descriptively.

Concomitant medications will be coded with the World Health Organization-Drug Dictionary (WHO-DD). The number and percentage of participants who receive concomitant medications will be summarized by WHO-DD Anatomical Therapeutic Chemical category and PT. At each level of summarization, a participant is counted once if he/she reports one or more medications at that level.

9.3.4 Pharmacokinetic Analyses

Serum concentrations will be summarized descriptively by visit.

Individual serum concentration vs. actual time profiles for each participant, as well as the mean $(\pm SD)$ serum concentration versus scheduled time profiles, will be presented graphically.

9.3.5 Pharmacodynamic/Immunogenicity Analyses

Descriptive summaries will be presented by visit for changes in pDC levels and ADA rate will be summarized descriptively.

9.3.6 Exploratory Analyses

The exploratory analyses will be detailed in the SAP.

9.3.7 Planned Analyses

The primary analysis will be performed when the last participant has completed Week 24 or withdraws prior to the scheduled Week 24 visit. All available data at the time of the data cut-off (including data collected after Week 24) will be included in the primary analysis.

The final analysis will be performed when all participants have completed trial.

Page 60 of 70

10 REGULATORY, ETHICAL, AND TRIAL OVERSIGHT CONSIDERATIONS

10.1 Local Regulations/Declaration of Helsinki

This trial will be conducted in accordance with the ethical principles that have their origin in the Declaration of Helsinki and that are consistent with ICH Tripartite Guideline for GCP and the applicable laws and regulations of the country in which the research is conducted, whichever affords the greater protection to the individual.

10.2 Ethical Review

It is the understanding of the sponsor that this protocol (and any amendments) as well as appropriate consent procedures, will be reviewed and approved by a research ethics board (REB)/ institutional review board (IRB). This board must operate in accordance with the current federal regulations. For sites with a local ethics committee, a letter or certification of approval will be sent by the investigator to the sponsor (or contract research organization [CRO]) before initiation of the trial and also whenever subsequent modifications to the protocol are made.

10.3 Informed Consent Process

An ICF describing in detail the trial treatment, trial procedures, and risks will be given to the participant, along with an assent form when required.

It is the responsibility of the investigator, or a person designated by the investigator (if acceptable by local regulation), to obtain written informed consent from each individual participating in this trial, after adequate explanation of the aims, methods, objectives, and potential hazards of the trial.

Informed consent is a process that is initiated prior to the individual's agreeing to participate in the trial and continues throughout the individual's trial participation. Consent forms will be IRB/REB approved, and the participant will be asked to read and review the document. The investigator will explain the research trial to the participant and answer any questions that may arise. A verbal explanation will be provided in terms suited to the participant's comprehension of the purposes, procedures, and potential risks of the trial and of his or her rights as a research participant. Participants will have the opportunity to carefully review the written consent form and ask questions prior to signing. The participants should have the opportunity to discuss the trial with their family or surrogates or think about it prior to agreeing to participate.

The participant will sign the informed consent document prior to any procedures being done specifically for the trial. Participants must be informed that participation is voluntary and that they may withdraw from the trial at any time for any reason, without prejudice. A copy of the signed informed consent document will be given to the participants for their records. The informed consent process will be conducted and documented in the source document (including the date), and the form signed, before the participant undergoes any trial-specific procedures.

The rights and welfare of the participants will be protected by emphasizing to them that the quality of their medical care will not be adversely affected if they decline to participate in this trial.

If new safety information results in significant changes in the risk/benefit assessment, or if any new information becomes available that may affect the willingness of a participant to continue to participate, the consent form should, if necessary, be reviewed and updated by the IRB/REB. All participants (including those already being treated) should be informed of the new information, given a copy of the revised form, and asked to give their consent to continue in the trial.

10.4 Trial Discontinuation and Closure

This trial may be temporarily suspended or prematurely terminated if there is sufficient reasonable cause. Written notification, documenting the reason for trial suspension or termination, will be provided by the suspending or terminating party to trial participants, investigators, the sponsor, and regulatory authorities. If the trial is prematurely terminated or suspended, the principal investigators will promptly inform trial participants and the IRB/REB, and will provide the reason(s) for the termination or suspension. Trial participants will be contacted, as applicable, and be informed of changes to trial visit schedule.

Circumstances that may warrant termination or suspension of the trial include, but are not limited to the following:

- Determination of unexpected, significant, or unacceptable risk to participants
- Insufficient compliance to protocol requirements
- Data that are not sufficiently complete or evaluable
- Scientific or corporate reasons

The trial may resume once concerns about safety, protocol compliance, and data quality are addressed and satisfy the sponsor, IRB/REB, Health Canada, and/or FDA.

10.5 Confidentiality and Privacy

Participant confidentiality and privacy is strictly held in trust by the participating investigators, their staff, and the sponsor and their interventions. This confidentiality is extended to cover testing of biological samples in addition to the clinical information relating to participants. Therefore, the trial protocol, documentation, data, and all other information generated will be held in strict confidence.

The investigator must assure that the participants' anonymity will be maintained and that participants' identities are protected from unauthorized parties. On case report form (CRF) or other documents submitted to the sponsor, participants should not be identified by their names, but by an identification code. The investigator should keep a participant log relating codes with the names of participants. The investigator should maintain in strict confidence documents not for submission to Horizon Therapeutics Ireland DAC (e.g., participants' written consent forms).

All research activities will be conducted in a setting as private as possible.

The trial monitor, other authorized representatives of the sponsor, and representatives of the IRB,

regulatory agencies, or pharmaceutical company supplying IP may inspect all documents and records required to be maintained by the investigator, including but not limited to, medical records (office, clinic, or hospital) and pharmacy records for the participants in this trial. The clinical trial site will permit access to such records.

The trial participant's contact information will be securely stored at each clinical site for internal use during the trial. At the end of the trial, all records will continue to be kept in a secure location for as long a period as dictated by the applicable legal or regulatory requirements, the reviewing IRB, institutional policies, or sponsor requirements.

10.6 Clinical Monitoring

Clinical site monitoring will be conducted to ensure that the rights and well-being of trial participants are protected; that the reported trial data are accurate, complete, and verifiable; and that the conduct of the trial is in compliance with the currently approved protocol/amendment(s), ICH GCP guidelines, and with applicable regulatory requirement(s). Centralized monitoring, which consists of remote review of accumulating data from all sites, will be performed as detailed in the Centralized Monitoring Plan.

10.7 Quality Assurance and Quality Control

Each clinical site will perform internal quality management of trial conduct, data and biological specimen collection, documentation, and completion.

Quality control (QC) procedures will be implemented beginning with the data entry system, and data QC checks, which will be run on the database, will be generated. Any missing data or data anomalies will be communicated to the site(s) for clarification/resolution.

During the trial, the sponsor or its representative will conduct monitoring visits at regular intervals. The monitoring visits will be conducted to ensure protocol adherence, quality of data, accuracy of entries on the eCRFs, IP accountability, compliance with regulatory requirements, and continued adequacy of the trial site and its facilities.

The site may be audited, monitored, or inspected by a quality assurance officer named by the sponsor, by the REB or IRB, and/or by the regulatory authorities. The investigator will be given notice before an audit occurs and will be expected to cooperate with any audit and provide assistance and documentation (including source data) as requested. The trial site will provide direct access to all trial-related sites, source data/documents, and reports for the purpose of monitoring and auditing by the sponsor and inspection by local and regulatory authorities.

10.8 Data Handling and Record Keeping

Data collection is the responsibility of the clinical trial staff at the site under the supervision of the site investigator. The investigator is responsible for ensuring the accuracy, completeness, legibility, and timeliness of the data reported.

The investigator must maintain adequate and accurate records to enable the conduct of the trial to be fully documented and the trial data to be subsequently verified. These documents should be classified into two separate categories: investigator's study files and participant clinical source documents.

The investigator must maintain source documents for each participant in the trial. These source documents will consist of case and visit notes (clinical medical records) containing demographic and medical information and the results of any tests or assessments. All information on the eCRFs must be traceable to the source documents in the participant's file. Data not requiring a written or electronic record will be defined before trial start and will be recorded directly on the eCRFs, which will be documented as being the source data.

The records should be retained by the investigator according to ICH guidelines, local regulations, or as specified in the Clinical Trial Agreement, whichever retention period is longer.

Participant data will be entered by site personnel using Medidata Rave, a web-based electronic data capture (EDC) and reporting system. This application will be set up for remote entry. Medidata is the developer and owner of Rave EDC. The EDC software has been fully validated and conforms to Title 21 of the Code of Federal Regulations, Part 11 requirements. Investigator site staff will not be given access to the EDC system until they have been fully trained. Designated investigator staff will enter the data required by the protocol into the eCRFs using this web-based application. Automatic validation programs check for data discrepancies in the eCRFs and, by generating appropriate error messages, allow modification or verification of the entered data by the investigator staff before confirming the data. The investigator must certify that the data are complete and accurate by applying an electronic signature to the eCRFs.

The data collected will be encoded and stored electronically in a database system. Validated data may subsequently be transferred to the sponsor.

10.9 Biological Specimens and Data

Study data are protected by the use of a sample identification (SID) number, which is a number specific to the participant. The investigator is in control of the information that is needed to connect a study sample to a participant; a participant may withdraw consent at any time by notifying the investigator. If consent is withdrawn, any samples collected prior to that time may still be given to and used by the Sponsor, but no new data or samples will be collected unless specifically required to monitor the safety of the participant.

Leftover samples stored for future research with participant consent will be labeled with a sample identification number. If the participant consents to have his/her samples used for future research, this additional research may not start immediately and may start at any time during the storage period. The participant's sample(s) will be stored by the Sponsor with similar samples in a secure laboratory. The participant's samples will not be kept for more than 15 years after the end of the study in which they were collected. If the participant chooses not to allow his/her study samples to be used for future research, the samples will be destroyed by the Sponsor once they are no longer required for the main study. If future use consent is withdrawn, the Sponsor and the investigator will ensure that the participant's sample(s) are destroyed unless the identification number has been

removed and the participant can no longer be linked to any samples. However, if the participant's sample has already been used for research, the Sponsor is not required to destroy the results of this research. In this case, only the remaining sample(s) will be destroyed.

10.10 Protocol Deviations

A protocol deviation is any noncompliance with the clinical trial protocol requirements. The non-compliance may be either on the part of the participant, the investigator, or the trial site staff. As a result of deviations, corrective actions are to be developed by the site and implemented promptly. The CRA must ensure that a prompt action is taken to secure compliance. If a non-compliance that significantly affects or has the potential to significantly affect human participant protection or reliability of trial results is discovered, the CRO and the Sponsor should perform a root cause analysis and implement appropriate corrective and preventive actions

Protocol deviations must be sent to the reviewing IRB per their policies. The investigator is responsible for knowing and adhering to the reviewing IRB requirements.

10.11 Publication Policy

The publication policy will be addressed in the Research and Financial Agreement, and all details outlined in the agreement will apply to this protocol. The trial will be registered on ClinicalTrials.Gov prior to the first participant being dosed.

1 INTRODUCTION

This document describes the statistical analysis for protocol HZNP-DAX-201, a phase 2a, open label, proof-of-concept trial of daxdilimab for the treatment of moderate-to-severe alopecia areata (AA).

Statistical Analysis Plan

2 TRIAL OVERVIEW

2.1 Trial Objectives and Endpoints

The objectives and corresponding endpoints are listed in Table 1 below:

Table 1Trial Objectives and Endpoints

Primary Objectives	Endpoints		
To evaluate the effect of daxdilimab on reducing hair loss at Week 24 in participants with AA.	Percent change from baseline in Severity of Alopecia Tool (SALT) score at Week 24.		
Secondary Objectives	Endpoints		
To evaluate the effect of daxdilimab on reducing hair loss through 9 months of treatment in participants with AA.	 Percent change from baseline in SALT score at Weeks 12-20; 28-36. Proportion of participants who achieve ≥50% reduction in SALT from baseline at Weeks 12-36. Proportion of participants with absolute SALT score ≤ 10, 20, 30, 50 at Weeks 12-36. 		
To evaluate the post-treatment duration effect of daxdilimab on reducing hair loss in participants with AA.	 Percent change from baseline in SALT score at Weeks 40-48. Proportion of participants who achieve ≥50% reduction in SALT from baseline at Weeks 40-48. Proportion of participants with absolute SALT score ≤ 10, 20, 30, 50 at Weeks 40-48. 		
To characterize the PK, PD, and immunogenicity of daxdilimab.	 Daxdilimab concentrations. Change from baseline in plasmacytoid dendritic cells (pDCs). Anti-drug antibody (ADA) rate. 		
To evaluate the safety and tolerability of daxdilimab.	Incidence of adverse events (AEs), serious adverse events (SAEs), and adverse events of special interest (AESIs).		

Statistical Analysis Plan

Table 1Trial Objectives and Endpoints

To characterize the PD of daxdilimab.	Change from baseline in blood biomarkers.
Abbreviations: AA, Alopecia Areata; ADA, anti-drug antibody; AE, adverse event; AESI, adverse event of special interest;	

PD, pharmacodynamic; pDC, plasmacytoid dendritic cell; PK, pharmacokinetic; SAE, serious adverse event; SALT, Severity of Alopecia Tool.

2.3 Sample Size

A total of up to 30 participants will receive daxdilimab in the trial. The sample size was determined by the need to evaluate potential efficacy, safety and tolerability, and PK/PD. No formal power calculation was performed.

The mean percent reduction from baseline in SALT score was 58% in 4 mg group at Week 36 in Eli Lilly's phase 2 AA trial (n=28) (King B, Ko J, Forman S, et al., 2021). The lower bound of the 95% confidence interval was about 42%. With 30 participants, if we observe a mean percent reduction from baseline in SALT score of 58% at Week 24, there is about 98% confidence that the mean percent reduction from baseline is at least 42%. The estimated confidence level that true mean percent reduction from baseline in SALT score is above a cutoff for an observed mean is provided in Table 2.

Table 2Confidence level that true mean percent reduction from baseline in SALT
score is above a cutoff for an observed mean

	Observed		Confidence that mean is	5
n	Mean % reduction	≥35%	≥42%	≥45%
30	50%	0.97	0.85	0.74
	55%	>0.99	0.95	0.90
	58%	>0.99	0.98	0.95

The proportion of patients achieving SALT ≤ 20 at Week 36 in 4 mg group was 33% and 35% in two Eli Lilly's phase 3 AA trials. The lower bound of the 95% confidence interval was about 27%. The estimated confidence level that true proportion of participants achieving SALT ≤ 20 is above 27% and other cutoffs for an observed response rate is provided in Table 3.

Table 3	Confidence level that true proportion of participants achieving SALT ≤ 20
	is above a cutoff for an observed response rate.

	Observed	Confidence that response rate is		
n	response rate	≥20%	≥25%	≥27%
30	9 (30%)	0.87	0.67	0.58
	11(36.7%)	0.97	0.89	0.84
	12(40%)	0.99	0.95	0.92
	13(43.3%)	0.99	0.98	0.96
	15(50%)	0.99	0.99	0.99

3 PLANNED ANALYSES

3.1 Primary Analysis

The primary analysis will be performed when all participant have completed Week 24 or withdraws prior to the scheduled Week 24 visit. All available data on or before the data cut-off (including data collected after Week 24) will be included in the primary analysis.

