4.1.3 Missing Data

In general, missing data will not be imputed unless methods for handling missing data are specified.

4.2 **Protocol Deviations**

The protocol deviations are reviewed and categorized as major and minor prior to the database lock. The number and percentage of participants with major protocol deviations by

Daxdilimab (HZN-7734) HZNP-DAZ-201 Statistical Analysis Plan

deviation reason (eg, nonadherence to study drug, violation of select inclusion/exclusion criteria) will be summarized. A by-participant listing will be provided for all protocol deviations.

A by-participant listing will be provided for those participants who did not meet at least one eligibility (inclusion or exclusion) criterion. The listing will present the eligibility criterion (or criteria if more than one deviation) that participants did not meet and related comments, if collected.

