4.7.1.4 Handling Plan for Missing Data

Missing visits, due to skipped visits or early dropout of study, will be imputed using the last observation carried forward (LOCF).

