4.7.2 Secondary Efficacy Endpoints and Analyses

4.7.2.1 Secondary Efficacy Endpoints

The secondary efficacy endpoints are as follows:

- Percent change from baseline in SALT score at Weeks 12-20, 28-36, and Weeks 40-48.
- Proportion of participants who achieve ≥ 50% reduction in SALT from baseline at Weeks 12-36 and Weeks 40-48.
- Proportion of participants with absolute SALT score $\leq 10, 20, 30, 50$ at Weeks 12-36 and Weeks 40-48.

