4.7.2.2 Secondary Efficacy Analyses

The continuous secondary efficacy endpoints will be summarized in the same way as the primary efficacy endpoint, including handling plan for prohibited medication use, treatment discontinuation and missing data (Section 4.7.1.3 and Section 4.7.1.4). Spaghetti plots of SALT score by participant over time will be presented. In addition, percent change from baseline in SALT score over time will be analyzed by baseline IFN gene signature levels (high versus low).

The binary secondary efficacy endpoints will be summarized descriptively using frequencies and percentages. A 2-sided 95% confidence interval will be calculated for the percentage. The participants will be considered non responder after administration of the prohibited medications that are considered to be effective for treatment of AA. The data collected after discontinuation of study treatment will be included in the analyses. Missing visits due to skipped visits will be imputed using the last observation carred forward (LOCF), and the participants will be considered non-responders after early dropout of study.

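### As written, the Week 24 primary-analysis report counts early dropouts at every later visit but continuing participants only at visits they have reached, which understates binary response at Weeks 28-48

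*SAP*

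**What the plan says.** SAP 3.1 sets the trigger: "The primary analysis will be performed when all participant have completed Week 24 or withdraws prior to the scheduled Week 24 visit". It then admits later data: "All available data on or before the data cut-off (including data collected after Week 24) will be included in the primary analysis". Protocol 9.3.7 says the same: "All available data at the time of the data cut-off (including data collected after Week 24) will be included in the primary analysis".

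The secondary endpoints in SAP 4.7.2.1 run well past Week 24, for example "Proportion of participants who achieve ≥ 50% reduction in SALT from baseline at Weeks 12-36 and Weeks 40-48". Weeks 28-36 serve the nine-month objective and Weeks 40-48 the objective on duration after treatment.

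Three rules decide who is counted at those visits:

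- **Binary endpoints (SAP 4.7.2.2):** "the participants will be considered non-responders after early dropout of study".
- **Continuous endpoints (SAP 4.7.1.4, applied to the secondary endpoints by 4.7.2.2):** "Missing visits, due to skipped visits or early dropout of study, will be imputed using the last observation carried forward (LOCF").
- **Everything else (SAP 4.1.3):** "missing data will not be imputed unless methods for handling missing data are specified".

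Participants who stop treatment but stay in the trial contribute their observed data (SAP 4.7.1.3 and 4.7.2.2), so only leaving the study triggers the dropout rules.

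**The concern.** When the last participant reaches Week 24, early enrollees may be at Week 48 while late enrollees have not reached Week 28. The dropout rules have no end point, so a participant who left at, say, Week 10 already has a non-responder status or a carried-forward SALT value for Week 48. A continuing participant whose Week 48 visit lies in the future has neither skipped it nor dropped out. The no-imputation default then applies and that person is missing from the table.

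Each visit after Week 24 is therefore summarized on all the dropouts but only some of the continuing participants, and the dropout share rises with visit number. For response rates the resulting decline is steepest at Weeks 40-48, where a reader is looking for relapse after the last dose. The trial has one arm and no randomization (Protocol 6.3), so no control curve would reveal the artefact. The SAP's handling of prohibited-medication users (worst value, or non-responder) likewise has no due-date limit.

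**Working it through.** **The plan's own figures.** The documents give no figure for this effect. The sample-size tables in SAP 2.3 do reproduce. Back-calculating the SD as (58 − 42)/1.96 × √28 = 43.2 gives 0.979 against the stated 0.98 in Table 2. The exact binomial for 9/30 gives 0.871, 0.674 and 0.577 against 0.87, 0.67 and 0.58 in Table 3. Neither table depends on this point.

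**Inputs.** N = 30 is from SAP 2.3 ("A total of up to 30 participants will receive daxdilimab in the trial"). The rest are assumptions: d dropouts, all before Week 24; even enrolment over A weeks; cut-off at the last enrollee's Week 24; visits at four-week steps; response p = 40% among continuing participants, constant over time and unrelated to enrolment date.

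**Formulas, binary endpoints.**

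- Share of continuing participants who have reached Week w: f = max(0, 1 − (w − 24)/A).
- Rate shown under the literal rules: p·f·(30 − d) / [f·(30 − d) + d].
- Rate once everyone is followed: p·(30 − d)/30.

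Whenever d > 0, p > 0 and f < 1, the first rate is below the second, because the dropouts stay whole while the continuing group shrinks.

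**Results for d = 3.** The fully followed rate is 0.4 × 27/30 = 36.0% at every visit.

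| Week | A = 26 | A = 36 | A = 52 |
|---|---|---|---|
| 24 | 36.0% | 36.0% | 36.0% |
| 28 | 35.4% | 35.6% | 35.7% |
| 36 | 33.2% | 34.3% | 35.0% |
| 40 | 31.0% | 33.3% | 34.5% |
| 44 | 27.0% | 32.0% | 33.9% |
| 48 | 16.4% | 30.0% | 33.2% |

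For example, at Week 48 with A = 36, f = 1 − 24/36 = 1/3. Then 9 continuing participants and 3 dropouts are counted, giving 3.6/12 = 30.0%. With A = 26, only about 2.1 continuing participants stand beside 3 dropouts.

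**Other dropout numbers, Week 48.**

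- d = 2: 20.7%, 32.9% and 35.3% for A = 26, 36 and 52, against 37.3%.
- d = 6: 9.4%, 22.9% and 27.3%, against 32.0%.
- d = 0: 40.0% wherever anyone has reached the visit, so no distortion.

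**Percent change in SALT.** Let m be the continuing participants' mean reduction and L the dropouts' carried-forward mean. The mean shown is [m·f·(30 − d) + L·d] / [f·(30 − d) + d]. With m flat at 58% (the reference mean in SAP 2.3), d = 3 and A = 26:

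| L | Fully followed | Shown at Week 48 |
|---|---|---|
| 0% | 52.2% | 23.7% |
| 20% | 54.2% | 35.5% |
| 58% | 58.0% | 58.0% |
| 70% | 59.2% | 65.1% |

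If the effect really is lost (m falling from 58% at Week 36 to 34% at Week 48) and L = 50%, Week 48 shows 43.5% against a fully followed 35.6%, so part of the loss is hidden. The direction is not fixed.

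**Sensitivity analyses.** The binary one (SAP 4.7.2.3) keeps dropouts as non-responders and so keeps the distortion. The continuous one imputes nothing for missing visits (SAP 4.7.1.5, extended to the secondary endpoints by 4.7.2.3) and so avoids it.

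**The case against.** The strongest reply is that this is silence rather than a rule. SAP 3.1 speaks of data available by the cut-off, and a Week 48 status for someone whose Week 48 date lies beyond it is arguably not such data. A symmetric reading, in which a visit not yet due is missing for nobody, removes the problem. Visit windows and presentation are left to a Statistical Programming Plan that is not part of these documents. This stands in part: the effect follows from literal application, and a careful programmer might avoid it. However, the SAP sets efficacy imputation itself, and a dropout's non-responder status is fixed by an event already known at the cut-off. Extending LOCF to continuing participants' future visits would be no remedy, since on-treatment values would be carried into Weeks 40-48 and could mask relapse.

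The consequence is also limited. The affected endpoints are secondary and descriptive, with no test attached. The SAP plans spaghetti plots and reports n with continuous summaries. Participants who stop treatment are still followed, which should keep study dropout down. Sampling error is large: about 18 people would be counted at Week 36 with d = 3 and A = 26, and 5/18 has an exact 95% interval of 10% to 53%. All of this stands, and it limits the weight of the point. It does not remove a systematic error that moves in one direction with visit number.

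A reader might infer that SALT change is also biased towards no effect. The documents do not support that, because the direction depends on the dropouts' last values. A reader who assumes exactly 24-week accrual would find 0% response at Week 48. That is a boundary product (f = 1 − 24/24 = 0, so only dropouts are counted), not an expected result.

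**Conclusion.** The point holds for binary response at Weeks 28-48 in the primary-analysis report, on the rules as written. It requires at least one study dropout and some continuing participants who have not reached the visit, and it assumes that those who have reached it are representative. The understatement grows with visit number and can look like loss of effect after treatment. The binary sensitivity analysis does not correct it.

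The size cannot be fixed from the documents, which state neither dropout nor accrual. Under the assumptions shown, with 3 of 30 dropping out, a flat 36% appears at Week 48 as about 16%, 30% or 33% for 26-, 36- or 52-week accrual. A false relapse is thus possible but not certain.

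For percent change in SALT the conclusion is only that bias of uncertain direction can arise, with an unaffected sensitivity analysis alongside. It would be wrong to infer that the trial's main result is compromised. The Week 24 primary endpoint is due for everyone at the cut-off, and the final analysis (SAP 3.2) returns dropouts to their proper share.

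**What to change.** In SAP 3.1, 4.7.1.4, 4.7.2.2 and 4.7.2.3, state that at the primary analysis any participant (dropout, prohibited-medication user or continuing) enters the summary of a post-Week-24 visit only if that visit's scheduled date, counted from Day 1, is on or before the data cut-off. Apply LOCF, worst-value and non-responder imputation only to visits that were due, and show the number due at each visit as the denominator.

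Dropouts are then thinned in the same proportion as continuing participants: p·f·(30 − d) / [f·(30 − d) + f·d] = p·(30 − d)/30. In the example this restores 36.0% at every visit with anyone due, provided dropout is unrelated to enrolment date.

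The cost is a few sentences, one derived flag for visits due by the cut-off, and smaller denominators at late visits in that report. No new data are needed, and the final analysis is unchanged.
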